## 4 INVESTIGATIONAL PLAN

### 4.1 Study Design

This is a randomized, double-blind, placebo-controlled study to investigate the efficacy, safety, tolerability, PK, and immunogenicity of KPL-716 administered SC in PN subjects experiencing severe pruritus.

The Phase 2b (Figure 1) portion of the study will consist of a 4-week Screening Period and a 16-week Double-Blind Period followed by a 36-week Open-Label-Extension (OLE) Period. Approximately 180 PN subjects experiencing severe pruritus will be randomized (at 1:1:1:1 ratio) into one of the following 4 arms: KPL-716 540 mg SC, once every 4 weeks (Q4W); KPL-716 360 mg SC, Q2W; KPL-716 120 mg SC, Q4W; or placebo SC, Q4W. A total of 4 doses of study drug will be administered during the Double-Blind Period to measure the efficacy, safety, and PK of KPL-716. The Phase 2b portion of the study will utilize a washout monotherapy design in which concomitant therapies that could impact pruritus or disease severity will be prohibited from designated windows through the end of the OLE Period, thus removing the confounding effect of these therapies on the assessment of KPL-716 efficacy. Should subjects experience an exacerbation of symptoms that is significant enough to warrant intervention, oral antihistamines and/or topical corticosteroids may be provided 4 weeks post-randomization, as outlined in the Pharmacy Manual. The days of rescue medication use will be recorded in an e-Diary and types and duration of rescue medications used will be recorded as a concomitant medication.

After the Double-Blind Period, all subjects will have the option to receive KPL-716 360 mg SC, Q2W during the OLE Period to evaluate long-term safety and PK. For subjects who complete the Double-Blind Period but choose not to participate in OLE, or who terminate earlier, an End of Study (EOS) Visit will be required 4 weeks following the date of last study drug dose.

An interim analysis may be performed after at least 50% of subjects have completed the Week 16 Visit. Additional details regarding the interim analysis, if performed, will be provided in the Statistical Analysis Plan (SAP) along with other analysis plan(s).

Subjects will follow the schedule below:

- Screening Period (minimum 7 days and maximum 28 days)
- Double-Blind Period (Day 1 [Baseline] to Week 16)
- Open-Label-Extension Period (End of Week 16 to Week 52)

The allowable visit window from Week 4 to Week 16 is  $\pm$  2 days and thereafter to Week 52 is  $\pm$  3 days.

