During the Screening Period, whole-body medical photographs will be taken (upper front, lower front, upper back, and lower back) without the face and with the genitals covered. In addition, a representative area of the disease will be determined by the PI at the Screening Visit, and medical photographs of this area will be taken and followed throughout the study. Medical photographs will be used for confirmation of diagnosis of PN as defined in the Study Manual and for assessment of disease severity over time. Subjects may be asked to return to the study site during the Screening Period for unscheduled visits for repeat screening procedures if needed.

Additional assessments at the Screening Visit may include those related to pruritus, sleep, quality of life, anxiety and depression, disease severity, etc. Subjects will be instructed on the required washout for specific excluded medications. The daily recordings (WI-NRS and rescue medication) will continue throughout the study for eligible subjects that proceed to dosing.

Collection of AEs and concomitant medications will begin after signing the ICF and will continue until the EOS Visit. For Schedule of Activities, please see [Appendix 1](#).

In an effort to minimize subject burden and/or risk during the COVID-19 pandemic, sites may offer to split the Screening Visit into two parts; a virtual preliminary Screening Visit in which some assessments may be performed [e.g. ICF, medical history, concomitant medications, subject questionnaires (completed electronically) and some eligibility criteria],

followed by an in-person visit in which all remaining eligibility assessments may be performed that require subjects to be physically present (e.g. blood collection for clinical laboratories, ECG, medical photography, vital signs, and disease severity assessments).

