### **4.7 Selection of Study Population**

#### **4.7.1 Inclusion Criteria**

1. Male or female aged 18 to 80 years, inclusive, at the time of consent.
2. Have a physician-documented diagnosis of PN that is confirmed by review of medical photography (as outlined in the Study Manual) during the Screening Period. Duration of PN (since the time of first PN nodule) must be at least 6 months from the time of first PN nodule to Day 1, as affirmed by the subject.
3. Have at least 20 nodules of approximately 0.5 to 2 cm at the Screening Visit and Day 1. The nodules must be pruritic and present on at least 2 different anatomical locations (not be localized), involve the extremities, with extensor extremity involvement greater than the flexor extremity involvement. Nodules on the head (face and scalp) are not counted as an anatomical location for eligibility criteria. Each arm, each leg, and trunk are considered different anatomical locations.
4. Subject has severe pruritus, defined as WI-NRS  $\geq 7$  at the Screening Visit and a mean weekly WI-NRS  $\geq 7$  for the week (7 consecutive days) immediately prior to randomization (at least 5 days of recordings) on eDiary.
5. PN-IGA score of  $\geq 3$  (on a scale of 0-4, in which 3 is moderate and 4 is severe) at Screening and Baseline Visits.
6. Sexually active female subjects must be:
  - postmenopausal, defined as at least 12 consecutive months post cessation of menses (without an alternative medical cause) and confirmed by a follicular stimulating hormone (FSH) test, or

- surgically sterile following documented hysterectomy, bilateral salpingectomy, bilateral oophorectomy or
- nonpregnant, nonlactating, and having agreed to use a highly effective method of contraception from the Screening Visit until 16 weeks after final study drug administration.
  - Note: highly effective methods of contraception include:
    - hormonal contraceptives associated with inhibition of ovulation (stable dose for at least 4 weeks prior to first dose)
    - intrauterine device
    - intrauterine system
    - double barrier methods of contraception (barrier methods include male condom, female condom, cervical cap, diaphragm, contraceptive sponge) in conjunction with spermicide.
    - tubal ligation
    - vasectomized male partner

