#### 4.7.2                   Exclusion Criteria

1. Use of the following medications within the indicated timeframe prior to Day 1 and does not agree to refrain from the use of the medications throughout the study (except these specified in the Pharmacy Manual):

- a. Systemic corticosteroids (IV/IM/oral): 4 weeks; Note: Intranasal corticosteroids, eye drops containing corticosteroids, and inhaled corticosteroids for stable medical conditions are allowed.
- b. Intralesional corticosteroids and intra-articular corticosteroids: 6 weeks
- c. Topical treatments for PN including but not limited to corticosteroids, calcineurin inhibitors, phosphodiesterase inhibitors, retinoids, calcipotriol, capsaicin, camphor, polidocanol, cannabinoids, gabapentin, or tars: 2 weeks
- d. Antihistamines: 2 weeks
- e. Immunomodulators (for example, cyclosporin, methotrexate, retinoids, azathioprine, mycophenolate, and thalidomide): 4 weeks
- f. Neuroactive drugs such as gabapentin and pregabalin: 4 weeks
- g. Cannabinoids: 2 weeks
- h. Opioid antagonists or agonists: 5 half-lives if known or 4 weeks
- i. Janus kinase inhibitors: 5 half-lives if known or 4 weeks
- j. Dupilumab: 8 weeks
- k. Any other marketed biologic: 5 half-lives or within 4 months of using rituximab
- l. Any investigational drug: 5 half-lives
- m. Phototherapy involving UVA, UVB, or excimer: 4 weeks
- n. Tanning salon use: 4 weeks
- o. Live attenuated vaccine: 12 weeks

2. Has received any investigational biologic or non-biologic drug that targets Oncostatin M, IL-31, IL-31 receptor  $\alpha$ , or Oncostatin M receptor  $\beta$  in the past 3 months.
3. Required rescue therapy for PN during the Screening Period or expected to require rescue therapy within 4 weeks following the Baseline Visit.
4. Has a significant exacerbation and/or skin eruption during the Screening Period (prior to the study drug administration) that requires a medical intervention.
5. Presence of scabies, insect bite, lichen simplex chronicus, psoriasis, acne, folliculitis, habitual picking, lymphomatoid papulosis, chronic actinic dermatitis, dermatitis herpetiformis, sporotrichosis, bullous disease and/or skin condition other than PN or atopic dermatitis unless approved by the Sponsor.
6. Plan to change emollients or moisturizers, or to have bath oil treatment for relief of pruritus during the course of the trial.

7. Presence of psychogenic pruritus or neuropathic pruritus at the Screening Visit.

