8. Presence of severe depression as indicated by PHQ-9 total score of  $\geq 20$  or item 9 score  $> 0$  at the Screening Visit or Day 1.
9. Presence of severe anxiety as indicated by GAD-7 score of  $\geq 15$  at the Screening Visit or Day 1.
10. Presence of severe chronic pain (e.g., back pain, migraine, osteoarthritis, etc., defined as  $\geq 7.0$  on 0 to 10 NRS scale with 0 being no pain and 10 being the worst pain possible) at the Screening Visit.
11. Presence of uncontrolled hyperthyroidism or hypothyroidism or uncontrolled diabetes defined as hemoglobin A1c  $> 7.5\%$ .
12. Presence or history of cancer or lymphoproliferative disease within 5 years prior to Screening Visit, with the exception of basal and squamous cell carcinoma of the skin or in situ carcinoma of the cervix successfully treated and considered controlled.
13. Presence or history of immune deficiency, or opportunistic infections.
14. Positive results for hepatitis B surface antigen (HbsAg) and/or hepatitis B anti-core antibody (anti-HBc) but negative results for anti-surface antibody (anti-HBs) at the Screening Visit.
15. Positive results for hepatitis C antibody unless patient received curative therapy and a negative viral load is documented.
16. Human immunodeficiency virus (HIV) infection or positive HIV serology at the Screening Visit.
17. Positive COVID-19 viral test at Screening Visit or suspected COVID-19 infection at Baseline Visit.
18. Subject is on hemodialysis or peritoneal dialysis.
19. Latent or active TB, as determined by a positive Quantiferon-based TB test result at Screening Visit.
20. Laboratory abnormalities that fall outside the windows below at the Screening Visit:
  - a. Alanine aminotransferase  $> 3 \times$  upper limit of normal (ULN)
  - b. Aspartate aminotransferase  $> 3 \times$  ULN
  - c. Gamma-glutamyl transferase  $> 3 \times$  ULN
  - d. Blood bilirubin  $> 2 \times$  ULN
  - e. Hemoglobin more than 1g/dL below the lower limit of normal for sex per the laboratory in which screening lab is performed
  - f. Platelet count  $< 150,000/\mu\text{L}$

g. Neutrophil count <1,500/ $\mu$ L

21. Major surgery within 12 weeks prior to Day 1 or has a major surgery planned during the study.
22. Has an active infection, including skin infection, requiring systemic treatment within 4 weeks and/or topical treatment within 2 weeks of Day 1. Subject has an active or chronic parasitic infection.

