23. Any medical or psychiatric condition which, in the opinion of the Investigator or the Sponsor, may place the subject at increased risk as a result of study participation, interfere with study participation or study assessments, affect compliance with study requirements, or complicate interpretation of study results.
24. Has a known hypersensitivity to KPL-716 or its excipients.
25. Has a known history of drug or alcohol abuse in the last 2 years prior to Day 1. Has more than eight drinks (5 ounces of wine, 12 ounces of beer or 1.5 ounces of liquor) weekly for females and 15 drinks weekly for males.
26. Has a positive urine drug screen for opiates, opioids, methadone, cocaine, phencyclidine, or amphetamines at the Screening Visit or Day 1. Exceptions may be made if a subject is on a medication for a stable concomitant condition that explains the positive drug screen result.
27. Has had a severe allergic reaction to any foods or medications including anaphylactic reactions, unless approved by the Sponsor.
28. For subject providing consent for the optional skin biopsy, presence or history of coagulation disorders, hypertrophic scar, or keloid, or currently under treatments with chronic anti-coagulants (aspirin  $\leq$  325mg/day is acceptable).

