## 6 CONCOMITANT THERAPIES AND OTHER RESTRICTIONS

### 6.1 Concomitant Medications

All subjects enrolled in this study must agree to follow the study protocol with respect to concomitant medications from the Screening Visit through the EOS Visit. The following medications are prohibited from designated timepoints before Day 1 (as noted in the exclusion criteria) and throughout the study.

- a. Systemic corticosteroids (IV/IM/oral). Note: Intranasal corticosteroids, eye drops containing corticosteroids, and inhaled corticosteroids for stable medical conditions are allowed.
- b. Intralesional corticosteroids and intra-articular corticosteroids
- c. Topical treatments for PN including but not limited to corticosteroids, calcineurin inhibitors, phosphodiesterase inhibitors, retinoids, calcipotriol, capsaicin, camphor, polidocanol, cannabinoids, gabapentin, or tars
- d. Antihistamines
- e. Immunomodulators (for example, cyclosporin, methotrexate, retinoids, azathioprine, mycophenolate, and thalidomide)
- f. Neuroactive drugs such as gabapentin and pregabalin
- g. Cannabinoids (other routes)
- h. Opioid antagonists or agonists
- i. Janus kinase inhibitors
- j. Dupilumab
- k. Any other marketed biologic
- l. Any investigational drug
- m. Phototherapy involving UVA, UVB, or excimer
- n. Tanning salon use
- o. Live attenuated vaccine

Topical corticosteroids and antihistamines may be provided 4 weeks after randomization as rescue medications for an exacerbation of symptoms that is significant enough to warrant intervention.

For further details refer to the Pharmacy Manual.

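### Exclusion criterion 1 uses 'and' where the design needs 'or': read literally, it admits a subject who used a listed drug inside its washout window but agrees to stop (minor)

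*Protocol*

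**What the plan says.** Criterion 1 appears with the same joining word in the Synopsis and in Protocol 4.7.2: "Use of the following medications within the indicated timeframe prior to Day 1 and does not agree to refrain from the use". Fifteen items follow (a to o), most with a washout time. There is an exception for medications specified in the Pharmacy Manual, which is not among the documents.

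Other sections state the washout without any condition on the subject's agreement:

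- Section 4.1: "concomitant therapies that could impact pruritus or disease severity will be prohibited from designated windows through the end of the OLE Period".
- Section 4.1.1: "Subjects will be instructed on the required washout for specific excluded medications".
- Section 6.1: "The following medications are prohibited from designated timepoints before Day 1 (as noted in the exclusion criteria) and throughout the study".
- SAP 4.6.6 describes the list in the same way, as running from before Day 1 and through the study. Its next sentence sends prohibited medication that affects efficacy to blinded medical review before database lock.

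Elsewhere in the same list, past and future conditions are joined by 'or'. Exclusion 3 reads "Required rescue therapy for PN during the Screening Period or expected to require rescue therapy within 4 weeks following the Baseline Visit" and exclusion 21 reads "Major surgery within 12 weeks prior to Day 1 or has a major surgery planned during the study".

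**The concern.** An eligibility criterion is applied as written. This one makes the washout times irrelevant to anyone who promises to stop, which is not the washout monotherapy design that Section 4.1 describes.

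The itch baseline is the mean of the daily scores from Day -7 to Day -1 (SAP 3.1). A drug still working in that week could lower the baseline. Once its effect had gone, the subject's percent change and the 4- and 6-point responder scores would look worse than they should. The stake is therefore distorted scores for the affected subjects and, if there were many, some loss in the efficacy comparisons.

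**Working it through.** **Logic.** Let A = used a listed drug inside its window, and B = does not agree to refrain.

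| Case | As written (A and B) | Sections 4.1, 4.1.1, 6.1 (A or B) |
|---|---|---|
| A and B | excluded | excluded |
| A, agrees to stop | **not excluded** | excluded |
| Washed out, will not refrain | **not excluded** | excluded |
| Neither | eligible | eligible |

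The third case is mostly caught by inclusion 10 (able to abide by study restrictions) and by the agreement in Section 6.1. The second is the real gap.

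**What other criteria cover in the second case.**

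- Inclusion 10 and the Section 6.1 agreement reach use from the Screening Visit on. Screening lasts at most 28 days.
- Inclusion 11 (stable co-morbidity treatment for 28 days) catches some listed drugs taken for another condition.
- Exclusion 2 covers investigational drugs against the same targets for 3 months.
- Exclusions 3 and 4 cover rescue therapy, or an exacerbation needing treatment, during Screening.
- Exclusion 26 covers some opioids: "Has a positive urine drug screen for opiates, opioids, methadone, cocaine, phencyclidine, or amphetamines at the Screening Visit or Day 1".

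None covers use before Screening in windows longer than 4 weeks: intralesional or intra-articular corticosteroid (6 weeks), dupilumab (8 weeks), live vaccine (12 weeks), rituximab (4 months). Dupilumab taken 6 weeks before Day 1, with agreement to stop, passes the text. Nor does any of them name maintenance therapy for prurigo nodularis that is stopped at entry.

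**Planned power.** Protocol 8.4 gives reductions of 53% and 30%, SD 35 and 38 per arm. The standardized effect is 23/35 = 0.657. A two-sided t-test at 0.05 with noncentrality 0.657 × √(38/2) has power 80.7%, which agrees with the stated 80%.

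**Cap on carry-over.** Inclusion 4 requires a weekly mean of at least 7 "for the week (7 consecutive days) immediately prior to randomization (at least 5 days of recordings) on eDiary". The scale stops at 10, so carry-over c can lower an enrolled subject's baseline by at most 3 points.

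**One affected subject.** Assume that carry-over has gone by Week 16 and that the planned relative reductions apply to off-drug itch B. With recorded baseline b = B − c, percent change is (0.70B − b)/b on placebo and (0.47B − b)/b on active.

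| B, c (b = B − c) | Placebo (planned −30%) | Active (planned −53%) |
|---|---|---|
| 8, 1 (b = 7) | −20% | −46% |
| 9, 2 (b = 7) | −10% | −40% |
| 10, 3 (b = 7) | 0% | −33% |
| 10, 1 (b = 9) | −22% | −48% |

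**Group level.** Assume a share p of 2% to 10% in every arm (0.9 to 4.5 of 45), all with b = 7. The mean difference is (1 − p) × 23 + p × 23B/7. The variance in each arm is (1 − p) × 35² + p × s² + p(1 − p) × δ². Here δ is that arm's mean shift, and s is the SD within affected subjects: either 35, or 35B/7 if it grows with the lower baseline.

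| p, c | s | Difference / SD | Effect | Power (n = 38) |
|---|---|---|---|---|
| 2%, 1 | 35 | 23.07/35.02 | 0.659 | 80.9% |
| 2%, 1 | 40 | 23.07/35.13 | 0.657 | 80.7% |
| 10%, 3 | 35 | 23.99/35.83 | 0.669 | 82.1% |
| 10%, 3 | 50 | 23.99/37.57 | 0.638 | 78.4% |

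**Responders.** Assume normal percent change. A k-point reduction needs a percent change of −100k/b or lower. The loss in the arm difference is p times the change in (active − placebo) for an affected subject. Worst cases, with c = 3 and p = 10%:

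- 4-point, s = 50: placebo falls from 38.8% to 12.7% and active from 64.5% to 31.4%. The difference falls from 25.7 to 18.7 points, and 10% of that change is 0.70 points. With s = 35 the loss is 0.65.
- 6-point, s = 35: placebo falls from 19.6% to 0.7% and active from 42.1% to 6.5%. The difference falls from 22.5 to 5.8 points, and 10% of that change is 1.67 points. With s = 50 the loss is 1.23.

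At p = 2% and c = 1 the losses are 0.03 to 0.07 points (4-point) and 0.11 to 0.13 points (6-point).

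**The case against.** The strongest reply is that nobody would read it literally. The literal reading would make every washout time pointless for a cooperative subject, and Section 6.1 says that its prohibition before Day 1 is the one noted in the exclusion criteria, which shows how the protocol understands its own rule. That stands as evidence of intent and is why this is minor. It does not change the criterion. Section 6.1 takes its timepoints from the same list, and an agreement that starts at Screening cannot govern earlier use.

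Some stronger readings are tempting but not supported:

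- *The SAP overlooks drug use before Day 1.* It does not. SAP 4.6.6 includes that period in the prohibited list it sends to blinded review. SAP 4.4 defines a deviation as any departure from the design or procedures in the protocol, and its three examples of important deviations are an open list.
- *Most of the 15 items have no other protection.* Inclusions 10 and 11 reach parts of several items. For some, such as live vaccine and tanning, no effect on itch is argued.
- *The treatment comparison is biased or underpowered.* Eligibility is settled before randomization, so affected subjects would be expected in all arms alike. The power range above includes small gains as well as losses.
- *Sites enrolled such subjects.* Nothing in the documents shows it, and the Pharmacy Manual, to which the criterion defers, cannot be checked.

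**Conclusion.** The point holds as a minor drafting error in an operative eligibility rule. The text admits a subject whom Sections 4.1, 4.1.1 and 6.1 would keep out, and no other criterion fully closes the gap.

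The likely effect is small: power of about 78% to 82% against 80.7%, and a loss of at most about 0.7 points (4-point) or 1.7 points (6-point) in the responder difference. Only the 3-point cap on carry-over comes from the documents. The shares affected, the size of carry-over within the cap, its disappearance by Week 16, the normal distribution and the two SD cases are assumptions. The textual conclusion depends on none of them.

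**What to change.** In the Synopsis and in Section 4.7.2, change the 'and' that precedes the clause on not agreeing to refrain to 'or'. Leave the windows and the Pharmacy Manual exception as they are. The SAP is also based on European and UK protocol versions that are not among the documents; check them for the same wording.

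The cost is one word in two places at the next amendment. It adds no restriction, because Section 6.1 already prohibits the drugs from the same timepoints, and no data, because prior medications are already recorded. If enrollment has finished, the change has little practical effect.

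No SAP change is required. At most, name use inside a window before Day 1 among the per-protocol deviations that SAP 2.4 already requires to be specified before unblinding.

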#### **4.8 Subject Number and Identification**

Each subject that signs the ICF and enters the Screening Visit will be assigned a unique screening number. The study site will record these numbers on a screening log, document reasons for screening failure or eligibility, whichever is applicable.

Once a subject qualifies for randomization, a unique treatment code will be obtained from a designated center via the interactive web response system (IWRS), which will assign the treatment for the subject. The randomization number will be kept on-file at study site and included in the electronic case report form (eCRF).

